9.2 Analysis population

- 1) Full analysis set (FAS): All patients diagnosed with distant metastasis or recurrence of esophageal cancer who received trial drug treatment and had at least one post-drug efficacy follow-up data were included in the full analysis set.
- 2) Per-protocol set (PPS): Subjects who met the main inclusion and exclusion criteria, completed the trial drug treatment and follow-up observation according to the protocol, and had complete survival data were included in the per-protocol set.
- 3) Safety analysis set (SS): All subjects who received trial drug treatment and for whom at least one post-dose safety data was available were included in the safety analysis set.

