1.1 Summary

[figure not shown]
Title:	A single-arm, prospective, single-center phase II clinical study to evaluate the efficacy and safety of nimotuzumab combined with concurrent chemoradiotherapy in elderly patients with locally advanced unresectable esophageal cancer
Study overview	The mortality rate of esophageal cancer is 77%, and this rate will be even higher in elderly patients with esophageal cancer. A safe and effective treatment method is urgently needed. Currently, Nimotuzumab has been approved for esophageal cancer indications in 9 countries. We plan to conduct a single-arm, prospective, single-center Phase II clinical study to explore the efficacy and safety of Nimotuzumab in elderly patients with locally advanced esophageal cancer. The study population is elderly patients with locally advanced unresectable esophageal cancer, and 50 people are planned to be enrolled.
Purpose	To evaluate the efficacy and safety of nimotuzumab combined with concurrent chemoradiotherapy in elderly patients with locally advanced unresectable esophageal cancer.
Endpoint	Primary endpoint: progression-free survival (PFS) Secondary endpoints: objective response rate (ORR), disease control rate (DCR), local disease control rate (LDCR), overall survival (OS), 1-year OS/PFS, 2-year OS/PFS, and AE/SAE incidence.
Study population	Inclusion criteria: All the following patients must be met to be included in this study 1.The subjects voluntarily participated in this study, signed the informed consent, had good compliance, and cooperated with the follow-up; 2.Age 75 and above , male or female;

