	
3.ECOG score 0-1;
 
4.Esophageal cancer confirmed by histology or cytology;
 
5.According to the Response Evaluation Criteria for Solid Tumors (RECIST 1.1), there is at least one measurable lesion, and the measurable lesion should not have received local treatment such as radiotherapy (lesions located in the previous radiotherapy area can also be selected as target lesions if they are confirmed to have progressed and meet the RECIST1.1 criteria);
 
6.Patients with stage II-IVB according to AJCC (8th edition, 2018) (IVB included metastasis to the celiac trunk or supraclavicular lymph nodes only) who are not suitable for or refuse surgery can tolerate concurrent chemoradiotherapy and targeted therapy;
 
7.Expected survival time ≥ 12 weeks;
 
8.The major organs function normally, meet the following criteria:
 
1)Blood test:
 
 a.HBG ≥ 90 g/L; b.ANC $\geq 1.5 \times 10^9$ /L; c.PLT $\geq 80 \times 10^9$ /L; 
2)Biochemical tests:
 
 a.ALB ≥ 30 g/L; b.ALT and AST ≤ 2.5 ULN; if there is liver metastasis, ALT and AST ≤ 5 ULN; c.TBIL ≤ 1.5 ULN; d.Plasma Cr ≤ 1.5 ULN or creatinine clearance (CCr) ≥ 60 ml/min; 
9.Echocardiographic assessment: left ventricular ejection fraction (LVEF) \geq lower limit of normal value (50%);
 
10.Female of childbearing age must agree to use contraceptive measures (such as intrauterine devices, birth control pills or condoms)

--	---

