4.1 Overall design

We plan to conduct a single-arm, prospective, single-center phase II clinical study to explore the efficacy and safety of nimotuzumab combined with concurrent chemoradiotherapy for elderly patients with locally advanced esophageal cancer. The

enrolled patients will receive nimotuzumab combined with S-1 and radiotherapy. This study includes a screening period, a treatment period, an efficacy follow-up period, and a survival follow-up period.

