5.1 Inclusion criteria

Patients must meet all of the following criteria to be eligible for this trial:

- 1)The patients voluntarily participated in this study, signed the informed consent, had good compliance, and cooperated with the follow-up;
- 2)Age 75 and above, regardless of gender;
- 3)ECOG score 0-1;
- 4)Esophageal cancer confirmed by histology or cytology;
- 5)According to RECIST 1.1 (see 12.2. Response Evaluation Criteria for Solid Tumors Version 1.1 for details), there is at least one measurable lesion, and the measurable lesion should not have received local treatment such as radiotherapy (lesions located in the previous radiotherapy area can also be

selected as target lesions if they are confirmed to have progressed and meet the RECIST 1.1 criteria);

6)Patients with stage II-IVB according to AJCC (8th edition, 2018) (IVB included metastasis to the celiac trunk or supraclavicular lymph nodes only) who are not suitable for or refuse surgery can tolerate concurrent chemoradiotherapy and targeted therapy;

7)Expected survival time \geq 12 weeks;

8)The major organs function normally, that is, they meet the following criteria:

●Blood test:

- a.HBG \geq 90 g/L;
- b.ANC \geq 1.5×10^9 /L;
- c.PLT \geq 80×10^9 /L;

●Biochemical tests:

- a.ALB \geq 30 g/L;
- b.ALT and AST \leq 2.5 ULN; if there is liver metastasis, ALT and AST \leq 5 ULN;
- c.TBIL \leq 1.5ULN;
- d.Plasma Cr \leq 1.5ULN or creatinine clearance (CCr) \geq 60ml/min;

9)Echocardiographic assessment: left ventricular ejection fraction (LVEF) \geq lower limit of normal value (50%);

10)Female of childbearing age must agree to use contraceptive measures (such as intrauterine devices, birth control pills or condoms) during the study and within 6 months after the end of the study; the serum or urine pregnancy test is negative within 7 days before study enrollment, and they must be non-breastfeeding patients; men must agree to use contraceptive measures during the study and within 6 months after the end of the study.

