9.1 Sample size estimation

This study is a single-arm, prospective, exploratory, single-center phase II clinical study. The sample size calculation was based on the primary study endpoint, namely, PFS assessed by the investigator.

The primary endpoint was the median PFS assessed by the investigator. Based on previous studies on radical radiotherapy for elderly esophageal cancer, the median PFS of elderly patients with locally advanced and inoperable esophageal squamous cell carcinoma after radical radiotherapy was 16 months. It was estimated that the median PFS of this study could reach 18.2 months. Using a one-sided test, $\alpha=0.05$, power=0.80, the sample size was calculated to be 41 cases. Considering the dropout rate of 20%, a total sample size of 52 subjects was required.

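### The full analysis set is restricted to metastatic or recurrent disease, although the trial enrols locally advanced disease

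*Protocol*

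**What the plan says.** Section 9.2 of the protocol opens the FAS definition with "All patients diagnosed with distant metastasis or recurrence of esophageal cancer who received trial drug treatment" and adds that at least one efficacy follow-up after treatment must exist. The other two sets in that section carry no disease condition:

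- The PPS is for "Subjects who met the main inclusion and exclusion criteria, completed the trial drug treatment and follow-up observation according to the protocol", with complete survival data.
- The safety set is for "All subjects who received trial drug treatment and for whom at least one post-dose safety data was available".

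The population is described differently elsewhere:

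- Section 1.1: "The study population is elderly patients with locally advanced unresectable esophageal cancer, and 50 people are planned to be enrolled".
- Section 4.1 gives the aim as to explore "efficacy and safety of nimotuzumab combined with concurrent chemoradiotherapy for elderly patients with locally advanced esophageal cancer".
- Section 5.1, criterion 6, accepts AJCC stage II to IVB, with the qualifier "IVB included metastasis to the celiac trunk or supraclavicular lymph nodes only".
- Section 9.1 takes its reference value from the statement that "the median PFS of elderly patients with locally advanced and inoperable esophageal squamous cell carcinoma after radical radiotherapy was 16 months".

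Section 9.3.1 assigns baseline data to the FAS, all efficacy measures to the FAS and the PPS, and safety to the safety set.

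**The concern.** The FAS wording describes a different disease setting from the one the trial recruits. It is not a missing detail that a statistical analysis plan would supply. It is a positive rule, and following it removes most of the intended population from the analysis.

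The set carries weight. It governs the baseline table and, with the PPS, the primary PFS analysis and every secondary efficacy endpoint. In a single-arm trial the only yardstick for PFS is the historical 16 months, which belongs to locally advanced inoperable disease. A PFS estimate from a metastatic or recurrent subset could not be set against it.

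**Working it through.** The point is textual, so the check sets the passages side by side and asks who is in the FAS.

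**1. Who can be enrolled (section 5.1).** Stage II, III, IVA, and IVB when the metastasis is confined to celiac trunk or supraclavicular nodes. Recurrent disease has a route in through criterion 5, under which "lesions located in the previous radiotherapy area can also be selected as target lesions if they are confirmed to have progressed".

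**2. Who then meets the FAS disease condition (section 9.2), read as a condition at entry.**

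| Enrolled patient | In the FAS as written? | In the PPS if compliant, with complete data? | In the safety set if treated, with safety data? |
|---|---|---|---|
| Stage II, III or IVA, no recurrence | No | Yes | Yes |
| Nodal IVB | Yes, if these nodes count as distant metastasis (the protocol does not say) | Yes | Yes |
| Recurrent disease | Yes | Yes | Yes |

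The first row is the group named in the title, summary, design section and sample size section. It is the group left out. The same row shows that the PPS is not contained in the FAS, which is incoherent for a full set and its per-protocol subset.

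**3. Does another reading rescue the wording?** The clause could mean metastasis or recurrence that appears after treatment. The FAS would then be selected on the outcome: patients who stay progression-free would be dropped from a PFS analysis, which pulls the estimate down. That reading is worse.

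**4. Does another section redefine the FAS?** No. Section 9.3.1 uses the set without redefining it, and section 9.3.2 only names Kaplan-Meier estimation.

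**5. Size.** The protocol gives no expected stage mix, so the size of the literal FAS cannot be derived. As illustration only, let *s* be the share with nodal IVB or recurrent disease, assumed to lie between 10% and 50%. The number meeting the disease condition is *s* × N:

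- N = 50 (section 1.1): 0.10 × 50 = 5; 0.50 × 50 = 25.
- N = 52 (section 9.1): 0.10 × 52 = 5.2; 0.50 × 52 = 26.
- N = 41 (section 9.1, before the dropout allowance): 0.10 × 41 = 4.1; 0.50 × 41 = 20.5.

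The figures for 50 and 52 are upper limits at each share, because the FAS also requires treatment and an efficacy follow-up.

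**The case against.** The strongest reply is that this is carried-over wording that no analyst would apply. The neighbouring set definitions lack the clause, and the protocol has other residue of this kind, such as references to randomization in sections 5.3 and 7.1.3 of a single-arm study. Efficacy is also analysed in the PPS, which is unaffected. A separate analysis plan, not shown, may define the set correctly.

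Much of this is fair. Literal application is unlikely, and the practical harm is more probably an ambiguous primary analysis set than a lost one. But the PPS is restricted to patients who complete treatment and follow-up, so it cannot stand in for the FAS. A correct analysis plan would leave the protocol sentence wrong and the two documents in conflict. In an open-label single-arm study, outcomes are visible as they accrue, so the primary population should not depend on an unwritten decision to ignore a clause.

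A second reply is that the eligibility criteria are not purely locoregional. Criterion 8 sets a transaminase limit for patients with liver metastasis, and exclusion 4 bars only some brain metastases. This stands as an observation: metastatic wording is not confined to section 9.2. It does not support the FAS clause, because criterion 6 still limits IVB to the named nodal sites, and stages II to IVA remain eligible in any case.

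Third, the 10% to 50% share has no source in the protocol. That is correct, and the conclusion does not rest on it. Likewise, the non-nested PPS is a consequence of the same clause and not a second error.

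**Conclusion.** The concern holds. The FAS definition in section 9.2 contradicts the population in sections 1.1, 4.1, 5.1 and 9.1 and, as written, leaves out every stage II to IVA patient without recurrence. It affects the baseline summary and all FAS efficacy results, including primary PFS.

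The number of patients lost cannot be stated from the protocol. The conclusion rests on the plain reading of the clause and on criterion 6 setting the eligible stages. It does not depend on whether nodal IVB counts as distant metastasis: if it does not, the literal FAS is smaller still. The text should be corrected before any analysis.

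**What to change.** Delete the condition on distant metastasis or recurrence from the FAS sentence in section 9.2. The FAS then consists of all patients who received trial treatment and have at least one efficacy follow-up after it, in parallel with the safety set. Any separate analysis plan should carry the same definition.

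Whether the remaining follow-up requirement suits a PFS endpoint is a separate question, because section 8.1.1 also counts death before progression and gives a date to patients with baseline imaging only. This deletion neither creates nor settles it.

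The cost is one sentence in a protocol amendment, with no extra patients, visits or data and no change to treatment.

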survival of patients with esophageal cancer without increasing the incidence of adverse events. Combined chemoradiotherapy/radiotherapy can be recommended for the treatment of patients with esophageal cancer. In 2019, Zhai Yirui et al. from the Cancer Hospital Chinese Academy of Medical Sciences published a study on nimotuzumab combined with chemoradiotherapy for the treatment of unresectable local advanced esophageal cancer ^[9]. The study included 26 newly diagnosed patients with esophageal cancer, with a median radiotherapy dose of 60 Gy, a median total nimotuzumab dose of 1200 mg, and an effective rate of 76.9%. The median follow-up was 30.5 months, and the median survival was 28.7 months. The 2-year and 3-year overall survival were 59.4% and 38.2%; the 2-year and 3-year progression-free survival were 51.4% and 33.3%. Another study conducted a retrospective analysis of the efficacy of nimotuzumab or cetuximab combined with chemoradiotherapy in the treatment of patients with locally advanced esophageal cancer ^[10]. The results showed that the ORR of the nimotuzumab + CRT group was 61%, slightly higher than that of the cetuximab + CRT group (43.5%), and the disease control rate of the nimotuzumab + CRT group was significantly higher than that of the cetuximab + CRT group ($P = 0.04$). Other survival analyses also showed that the median PFS of the nimotuzumab + CRT group was significantly longer than that of the cetuximab + CRT group (19.6 months vs 13.0 months, $p = 0.02$). The 1-year and 3-year OS of the nimotuzumab + CRT group were higher than those of the cetuximab + CRT group ($HR = 1.17$, $p = 0.23$).

At present, many studies have confirmed that nimotuzumab can improve the efficacy of esophageal cancer in the elderly. Common acute toxic reactions included esophagitis, pneumonia, leukopenia, gastrointestinal reactions, and thrombocytopenia. The incidence of Grade 3-4 adverse reactions was 17.4%, and no Grade 5 toxic reactions were observed. The median overall survival (OS) was 17 months, and the progression-free survival (PFS) was 10 months. The 2-, 3-, and 5-year OS and PFS were 30.4%, 21.7%, and 19.6%, and 26.1%, 19.6%, and 19.6%, respectively. This result confirms that nimotuzumab combined with radiotherapy is a safe and effective treatment for elderly patients who cannot undergo surgery. Li Lulu ^[11] randomly

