4.1.2 Treatment period

●Definition: First radiotherapy day W1D1 - last radiotherapy day W5D5

●Window period: treatment ± 2 days, imaging ± 7 days, pre-dose items -1 day.

●Content:

1)Before WxD1 administration

a.Body surface area (BSA);

b.Physical examination

c.Vital signs;

d.ECOG performance status score;

e.Blood samples and other laboratory evaluations (hematology and clinical chemistry);

f.Electrocardiogram (12 leads);

2)Administer nimotuzumab (see 6.1.2. Dosage and administration);

3)Administer Tegafur (see 6.1.2. Dosage and Administration);

4)Administer radiation therapy (see 6.1.2. Dosage and administration);

5)Observe and record adverse events;

6)Combined treatment;

7)Imaging examination: Review every 21 days after W1D1 (such as W1D22).

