8.1 Efficacy evaluation

The starting point of efficacy evaluation is the time when the subject first receives treatment

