8.1.1 Disease progression as the endpoint

- 1)The event endpoint was the time to disease progression in the subject;
- 2)If disease progression is confirmed but the time of disease progression

cannot be determined, the last imaging examination time of the subject without disease progression is used as the event endpoint;

3)For patients who died of any other cause before disease progression, the time of death of the subject will be used as the event endpoint;

4)For subjects who have not experienced disease progression or death (i.e., progression-free survival) at the time of analysis, the time of the last tumor assessment will be used as the event endpoint;

5)For subjects lost to follow-up, the time to the last tumor assessment without disease progression will be used as the event endpoint;

6)For subjects who only have baseline imaging examination, the time of baseline examination will be used as the event endpoint.

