9.3 Statistical Analysis

9.3.1 Statistical analysis plan

SPSS version 26.0 software was used for statistical analysis. Baseline data were analyzed according to the full analysis set, and all efficacy indicators were analyzed according to the full analysis set and the per-protocol set; safety analysis was performed using the safety analysis set.

Descriptive statistics were used to analyze all data, including demographic data, baseline, various efficacy evaluation indicators, and all safety data. Measurement data were expressed as mean \pm standard deviation or median and upper and lower quartiles, and count data were expressed as frequency or percentage. Dropout was defined as any reason that caused the subject to fail to complete the follow-up required by the protocol. For exclusion, dropout cases were statistically described one by one. The anti-tumor efficacy of nimotuzumab was analyzed in the full analysis set and the per-protocol set.

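### The FAS entry rule in 9.2 can drop a treated patient who dies before any post-drug assessment, a death that 8.1.1 makes a PFS endpoint; the resulting upward shift in median PFS is small

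*Protocol*

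**What the plan says.** Five statements in the protocol bear on this.

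- **Analysis set (9.2).** Among treated patients, those who "had at least one post-drug efficacy follow-up data were included in the full analysis set". The per-protocol set is stricter: it also asks for completed treatment and follow-up, and complete survival data.
- **Use of the sets (9.3.1).** "all efficacy indicators were analyzed according to the full analysis set and the per-protocol set". No other set is planned for efficacy.
- **Time origin (8.1).** "The starting point of efficacy evaluation is the time when the subject first receives treatment".
- **Death without progression (8.1.1 item 3).** "For patients who died of any other cause before disease progression, the time of death of the subject will be used" as the endpoint.
- **No post-baseline imaging (8.1.1 item 6).** "For subjects who only have baseline imaging examination, the time of baseline examination will be used as the event endpoint".

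Section 4.1.2 places the first on-treatment imaging at about day 22, with a window of 7 days either way. Section 9.3.2 estimates the median by Kaplan-Meier, and 9.1 sets it against a reference of 16 months.

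**The concern.** The endpoint rules and the set rule do not fit together. Section 8.1.1 starts the clock at first treatment, counts a death without progression, and gives a date for a patient with baseline imaging only. It therefore expects patients without any post-drug scan to be in the PFS analysis. Section 9.2 makes entry depend on something observed after treatment starts. A patient treated on day 1 who dies on day 10 has a PFS endpoint under item 3 but may not belong to the set in which PFS is analysed.

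In a randomised trial such a rule might act on both arms. Here there is one arm and a fixed historical reference, so losing early deaths would favour the treatment. Items 3 and 6 also overlap. The same patient has baseline imaging only and has died, and the two items give different dates. Widening the set alone would not be certain to keep the event.

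**Working it through.** **The plan's own number.** Section 9.1 takes 41 cases and 20% dropout: 41/0.80 = 51.25, rounded up to 52. That step reproduces, and 52 is used below. (The 41 does not follow from 16 versus 18.2 months in a one-sample exponential comparison: (1.645 + 0.842)²/ln(18.2/16)² gives 373 events. That is a separate matter and nothing here depends on it.)

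**Direction.** If the earliest event is a death with n patients at risk, it contributes a factor (n − 1)/n to the Kaplan-Meier curve. Removing the patient deletes that factor and leaves every later risk set unchanged, so S(t) is multiplied by n/(n − 1) > 1 from then on. More generally, removing a death at time u multiplies S(t) for t ≥ u by at least n/(n − 1), with n the number at risk at the first event. S(t) can fall only before u. If u precedes the median, the median therefore rises or stays the same. In 6,000 simulated data sets with 1 to 4 deaths in month 1 removed, the median was lower in 0, unchanged in 2,351 and higher in 3,649.

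**Size per patient.** Assume exponential PFS with median 16 months. Removing the earliest fraction p gives a median of 16 × (1 − log2(1 − p)).
- One of 52: 16 × 1.0280 = 16.45, a shift of 0.45 months.
- Two of 52: 16.91, a shift of 0.91 months.
- One of 52 with Weibull PFS: 0.30 months (shape 1.5) to 0.56 months (shape 0.8).

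These are smooth values. In one data set the median moves in whole event steps: the 26th event of 52 becomes the 27th whether one or two early deaths are removed. In 2,000 simulated trials the mean shift was 0.95 months for one removed and 0.94 for two, so about 0.47 per patient when two are removed.

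**Precision.** With all patients followed past the median, SE = √(0.25/52) / (0.5 × ln 2/16) = 0.0693/0.02166 = 3.20 months. So 0.45/3.20 = 0.14 of a standard error.

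**How many such deaths.** The protocol gives no rate. As an assumed range, take the two overall survival figures in 2.2 ("the median survival was 28.7 months" in one series, "The median overall survival (OS) was 17 months" in another) at a constant hazard up to day 22 (0.723 months).
- OS median 28.7: 1 − 2^(−0.723/28.7) = 1.73%, or 0.90 of 52; chance of none 40%; shift 0.40 months.
- OS median 17: 1 − 2^(−0.723/17) = 2.90%, or 1.51 of 52; chance of none 22%; shift 0.68 months.

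Eligibility (ECOG 0–1, expected survival of at least 12 weeks) argues for fewer.

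**Items 3 and 6.** In 20,000 simulated trials of 51 other patients plus one death on day 10, censoring that patient at the baseline date gave the same median as excluding the patient every time, and never a lower median than counting the death.

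**The case against.** The strongest reply is that a death is efficacy data. Section 8.1 handles death under efficacy evaluation, OS is a listed endpoint, and the schedule ticks survival follow-up at every treatment visit from day 1. On that reading nobody who dies is lost and the conflict disappears. This stands as a possible reading, so the exclusion is not certain. But the protocol does not state it, and 4.1.4 uses the term efficacy follow-up for a period that begins only after radiotherapy. Nor is this a detail left for the SAP: the protocol itself fixes the set, the endpoint rules and the link between them.

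It can also be said that item 6 is naturally the residual case, after items 1 to 3 have dealt with progression and death. That is probably what was meant, and one sentence would settle it.

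Four stronger readings are tempting and should not be drawn.
- *Any exclusion under this rule raises the median.* True only for deaths before the median. A patient who missed every scan and died later is also excluded; in a check of that case, removal lowered the median in 1,943 of 6,000 data sets.
- *The rule removes only early deaths.* It also removes living or lost patients with baseline imaging only. Their removal leaves the median unchanged if item 6 means censoring at baseline.
- *The rule inflates the type I error by a stated amount.* Section 9.1 mentions a one-sided test for the sample size only, and 9.3 plans descriptive and Kaplan-Meier estimates. With no named test there is no error rate to attach.
- *Nothing before the first post-radiotherapy review counts, so far more deaths are lost.* Section 9.2 does not tie its condition to the period in 4.1.4, and the scan at about day 22 is itself a post-drug assessment.

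The same sentence in 9.2 also refers to distant metastasis or recurrence, which does not match the locally advanced population. That is a separate fault; the arithmetic here takes all 52 treated patients as otherwise eligible for the set.

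**Conclusion.** The point holds in a limited form. Unless a death counts as an efficacy datum, 9.2 excludes from PFS a treated patient whose early death 8.1.1 item 3 counts. For deaths before the median, which covers any death before a scan due at about three weeks, the effect on the Kaplan-Meier median is upward or nil.

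The size is about 0.45 months per excluded patient (0.14 of a standard error), assuming 52 treated patients and exponential PFS with median 16 months. With the 50 patients named in the protocol summary it is 0.47. The number of such patients is unknown and may be zero. The range of 0.9 to 1.5 rests on borrowed survival figures: the 28.7-month series had 26 patients and is not described as elderly, and the 17-month series had a median PFS of 10 months, not 16.

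This would not by itself change the reading of an exploratory trial. The reason to act is that, for early deaths, the error runs in one direction, and whether they count should not be settled after the results are known. Severity: minor to should-fix.

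**What to change.** 1. In 9.2, define the primary analysis set for PFS and OS as all enrolled patients who received any study treatment, with no condition on post-baseline data.
2. In 8.1.1, state that item 3 prevails over item 6 for any patient known to have died, so that the death is an event at the date of death. Item 6 then applies only to patients with baseline imaging only who are not known to have died or progressed, and should say that they are censored at that date.

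Both changes are needed: the first brings the patient into the set, the second keeps the event.

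The cost is wording only, with no extra visits or data. The median PFS may come out slightly less favourable.

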7.1.1 Criteria for discontinuation of study intervention

In the event of any of the following circumstances, the subject must discontinue the study intervention

- 1)If a clinically relevant event occurs that seriously affects the safety of the subject, the investigator or sponsor considers it necessary to terminate the intervention;
- 2)Imaging examinations to determine disease progression;
- 3)The subjects received other study drugs or chemotherapy during the clinical study;
- 4)Lack of compliance by subjects;

- 5)The subject becomes pregnant during treatment;
- 6)Elective surgery.

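### The per-protocol set drops subjects who progress or die during treatment, which lifts its PFS median by about one month, yet it carries the primary endpoint beside the full analysis set

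*Protocol*

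**What the plan says.** **Membership of the PPS.** Protocol section 9.2 sets three conditions beyond eligibility, all known only after baseline: subjects who "completed the trial drug treatment and follow-up observation according to the protocol, and had complete survival data were included in the per-protocol set".

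**Use of the PPS.** Section 9.3.1 states that "all efficacy indicators were analyzed according to the full analysis set and the per-protocol set", and repeats the rule: "The anti-tumor efficacy of nimotuzumab was analyzed in the full analysis set and the per-protocol set". Only the baseline data are given to the full analysis set (FAS) alone. PFS is the primary endpoint, so the rule covers it.

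**Treatment and progression.** Section 4.1.2 defines the treatment period as "First radiotherapy day W1D1 - last radiotherapy day W5D5". Section 7.1.1 lists, among the circumstances in which a subject must stop the study intervention, "Imaging examinations to determine disease progression". Section 8.1 starts the efficacy clock at first treatment.

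**Subjects without an event.** Section 8.1.1 already supplies a date for each of them, for example: "For subjects lost to follow-up, the time to the last tumor assessment without disease progression will be used as the event endpoint". Section 8.1.2 does the same for death, using the last follow-up.

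**The FAS.** Section 9.2 restricts it to patients with metastatic or recurrent disease who received trial drug and "had at least one post-drug efficacy follow-up data were included in the full analysis set".

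**The concern.** A subject who progresses or dies within the first five weeks cannot complete treatment and so cannot enter the PPS. The reason for leaving is the primary endpoint itself. Those who stay are still timed from first treatment, so each brings a stretch of event-free time that membership guaranteed in advance (immortal time).

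A randomised trial would apply the same selection to both arms. Here there is one arm, and the benchmark is a historical median of 16 months. The planned improvement is small, so a modest shift matters.

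The condition on complete survival data adds a second problem. The protocol does not say what it means. If it removes lost or censored subjects, it contradicts sections 8.1.1 and 8.1.2, which keep such subjects by giving them a date.

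**Working it through.** The protocol gives no figure for the effect of the PPS rule, so there is none to reproduce. The yardstick is the planned gain in section 9.1: 18.2 − 16 = 2.2 months.

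**Inputs**
- True median PFS of 16 months, that is, no benefit over the benchmark (section 9.1).
- End of treatment at W5D5, which is day 4 × 7 + 5 = 33 (section 4.1.2). In months, L = 33 / 30.4375 = 1.08.
- 50 subjects (section 1.1). Section 9.1 has 52; the difference does not matter here.
- Assumption, not in the protocol: exponential PFS, with the same hazard during treatment as afterwards.

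**Share removed by treatment completion**
1 − 0.5^(L/16) = 1 − 0.5^(1.08/16) = 0.046, or 0.046 × 50 = 2.3 subjects.

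**PPS median**
For an exponential time, the median given survival past L is L + 16 = 1.08 + 16 = 17.1 months.

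**Against the planned gain**
1.08 / 2.2 = 0.49, so about half, with no drug effect.

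**Sensitivity to the cut-off**
- Section 4.1.4 labels the end of radiotherapy D29. Then L = 29 / 30.4375 = 0.95 and the median is 16.95 months.
- If early progression comes to light only at the scan due around day 22 (section 4.1.2), L = 22 / 30.4375 = 0.72. The share removed is 1 − 0.5^(0.72/16) = 0.031, or 1.5 of 50, and the median is 16.7 months.

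The shift is therefore about 0.7 to 1.1 months.

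**Simulation check**
The settings were 50 subjects, exponential PFS with median 16, 24 to 36 months of administrative follow-up, 20% random dropout by 24 months and a 35-day treatment period, with 6,000 runs. Follow-up and dropout pattern are assumptions.

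| Set | Median PFS (months) | One-sided rejection at 5% |
|---|---|---|
| FAS | 16.0 | about 4% |
| PPS, treatment completed | 17.1 | 8.5% |
| PPS, dropouts also removed | 15.2 | 2.4% |

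The rejection rates use an exponential log-hazard test against 16 months. Section 9.3 names no test, so they only illustrate. The last row shows why the undefined condition matters. A subject who drops out before an event has, on average, a longer true PFS than one whose event is seen. Removing dropouts therefore pulls the median down, and the net direction reverses.

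**The case against.** **Completing follow-up does not exclude later progressors.** A reader might infer that anyone who progresses or dies early fails to complete follow-up. Requiring event-free time through W9D5, or through the next 12-weekly visit, would give medians of about 18.0 or 20.8 months. The protocol does not support this. Section 4.1.4 ends efficacy follow-up at progression and section 4.1.5 ends survival follow-up at death or loss. A subject who progresses at month 4 has completed follow-up as planned. Only the selection through treatment completion has a textual basis.

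**Complete survival data need not mean an observed event.** A reader might take the phrase to drop every censored subject. Under that reading a true median of 18.2 months, with events counted to 24 months, would appear as about 9.3. The wording does not require it: an event-free subject followed to the analysis date can fairly be called complete. What stands is that the phrase is undefined.

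**Ranking can wait for the analysis plan.** A separate statistical analysis plan could name the primary set, and analysing both sets is conventional. Silence on rank alone would be no finding. The point here is the stated membership rule and its stated use for PFS.

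**The study is exploratory and imprecise.** Section 9.1 calls it exploratory, and sections 9.3.1 and 9.3.2 prescribe descriptive statistics and Kaplan-Meier estimates. With exponential PFS, a median of 18.2, 12 months of accrual and a further 24 months of follow-up, about 68% of 50 subjects, or 34, would have an event. A 95% interval for the median then spans a factor of exp(1.96/√34) = 1.40 each way, about 13.0 to 25.5 months. A shift of one month is small beside that. It is nevertheless systematic, and more subjects would not reduce it.

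**The FAS is no clean alternative.** This is right. As worded, the FAS requires metastatic or recurrent disease, which does not fit a locally advanced population, and post-drug efficacy data. Naming it primary unchanged would be worse.

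**Conclusion.** The point holds in a limited form. The PPS rule removes subjects because of an early primary-endpoint event while PFS is still timed from first treatment. With exponential PFS and a true median of 16 months, about 4.6% of subjects leave (about 2 of 50). The PPS median becomes about 17.1 months, about half the planned 2.2-month gain.

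The size rests on a constant hazard during treatment and on events being recognised before W5D5; with detection only at the day-22 scan it is nearer 0.7 month. This upward bias comes from the treatment-completion condition alone. The condition on complete survival data adds a bias whose direction depends on how it is read, so no net figure for the whole PPS definition can be given.

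**What to change.** - **Primary set for PFS:** all enrolled eligible subjects who received any study treatment. Correct the FAS wording in section 9.2 to match, by deleting the restriction to metastatic or recurrent disease and the requirement for post-drug efficacy data. Section 8.1.1 already has a rule for subjects with baseline imaging only.
- **PPS:** define it by eligibility and a pre-set minimum of treatment received, chosen by the sponsor before the data are seen. State that stopping treatment because of progression or death is not a protocol deviation.
- **Censored subjects:** delete the conditions on completed follow-up and complete survival data, and apply sections 8.1.1 and 8.1.2. Those sections call every date an event endpoint, so say which dates are censoring dates.
- **Role:** state in section 9.3.1 that the PPS analysis is supportive only. A PFS analysis from an end-of-radiotherapy landmark is optional.

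The cost is a few sentences of definition and a PPS estimate that may be slightly less favourable. No visit, assessment or treatment changes.
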